Extensive research in animal models has shown a benefit to using intravenous (IV) vitamin C in sepsis.^{4,5} It is a cofactor for multiple enzymatic functions.⁶ In addition, one study in particular found that critically ill patients, including those with sepsis have significantly lower levels of circulating vitamin C during their acute illness than their healthy counterparts. Furthermore, the investigators found critically ill patients who were administered an infusion of vitamin C every six hours maintained normal plasma levels for the largest amount of time.⁶ One study showed that critically ill patients required up to 3 grams per day of vitamin C just to return their plasma concentrations to normal baseline levels.⁷ Additional research indicates that critically ill patients are often thiamine-deficient which is frequently missed and not treated by their clinicians.^{8,9}

Marik et al. published a novel study implicating the use of IV vitamin C, vitamin B₁, and hydrocortisone resulted in a significantly lower mortality rate for their septic patients. His team explored the utility of these medications as compared to historical controls of their previously treated septic patients.¹⁰ This study, while novel and inspiring, was designed with the acceptance of multiple confounders and potential for bias including the retrospective nature, the lack of randomization, and the lack of blinding. We propose investigating the use of IV vitamins B₁ and C in a randomized, prospective trial, eliminating the potential for selection bias.

Hypotheses

[figure not shown]
1. Primary Hypothesis: Septic patients in the ICU who receive IV vitamins B₁ and C will demonstrate a decreased mortality rate compared to septic patients who do not receive IV vitamins B₁ and C.
2. Secondary Hypotheses: Patients receiving IV vitamins B₁ and C
 - a. will have shorter hospital length of stays (HLOS)
 - b. will have shorter ICU length of stays (ICU LOS)
 - c. will demonstrate a lower 30-day readmission rate
 - d. will have fewer ventilator days
 - e. will have fewer hours on vasopressors
 - f. in addition to IV hydrocortisone for refractory septic shock will have a more profound reduction in mortality when as compared to those receiving IV vitamins B₁ and C alone

g. who also record to higher Sequential Organ Failure Assessment (SOFA) scores will have a more significant reduction in mortality than patients who record lower SOFA scores

Objectives

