The objective of this study is to determine if the administration of IV vitamins B₁ and C are effective in decreasing the mortality rates of patients with severe sepsis or septic shock. In addition, we will investigate if there are benefits to those patients who also receive hydrocortisone in an effort to explore the synergistic relationship that vitamins B₁ and C have with hydrocortisone.

Overview of Study Design

Patient Selection Criteria

1. Inclusion Criteria: Patients admitted to the ICU at Saint Francis Hospital and Medical Center who are:
 - a. Between the ages of 18 and 90 years old
 - b. Have severe sepsis or septic shock
 - i. Severe sepsis and septic shock will be defined by the Surviving Sepsis 2012 guidelines¹¹
 - c. Weight more than 30 kg
 - d. Full code
2. Exclusion Criteria: Patients
 - a. Not diagnosed with severe sepsis or septic shock
 - b. Younger than 18 or older than 90 years old
 - c. Who are pregnant
 - d. Weigh less than 30 kg

- e. Currently on hemodialysis
- f. Not located in the ICU
- g. Do not resuscitate (DNR) or do not intubate (DNI), no escalation of care, or comfort measures only (CMO)

Enrollment/Randomization

Once identified, patients who meet inclusion criteria will be approached. The majority of patients are likely to be intubated and sedated at the time of their diagnosis of severe sepsis or septic shock. In these cases, the next of kin or consenting party will be approached for each patient. The providers in the ICU, mainly physician's assistants (PAs) and residents, always contact patient's family members for consent for central lines and other invasive procedures while in the ICU. The study staff will speak to this same consenting person (in person or on the phone) and will ask them about the potential enrollment of their loved one in the study. In the absence of documentation of a healthcare proxy or conservator (as is often the case with septic patients, as it is an unexpected illness), priority will be given to the patient's spouse, followed by an adult child, followed by a parent, followed by an adult sibling. .

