Prior to the recruitment process the pharmacy will enter numbers 1-120 in ascending order into a randomizing website. This randomly assigned each number to either placebo or intervention. Prior to recruitment, kits in blocks of 10, containing either the placebo or unmixed forms of vitamin B₁ and C are made and placed in identical packages labeled with their corresponding number. These numbers will be assigned in ascending order corresponding to the order in which they are consented. Once ordered by the providers the pharmacy will open the identical kits and, if it is the intervention, mix the vitamin B₁ and C for IV administration. This process will ensure the study coordinators, healthcare providers, and the patients remain blinded. Vitamins B₁ and C will be ordered for all patients in Epic, giving the impression that all of those

enrolled are in the intervention group. However half the kits will contain the intervention and half will contain the placebo. This is being done due to logistical issues with preparing and storing the vitamin B₁ and C. Having premade kits allows the pharmacy to more easily prepare and distribute the vitamin B₁ and C. These also need to be refrigerated and given limited space kits will be made in blocks of 10 to limit crucial storage space the pharmacy needs for other medications.

We plan to enroll 120 patients; 60 in the control arm and 60 in the intervention arm. Our current mortality rate is 35% at Saint Francis Hospital and Medical Center for patients with severe sepsis and septic shock. We expect our mortality rate to decrease to 30% with this intervention. We believe this is a reasonable expectation given that Marik et al. demonstrated that his intervention group's mortality rate dropped from 40.4% to 8.5% after a similar intervention.¹⁰ In order to demonstrate this difference, 120 patients are needed according to our power calculation.

Informed Consent/Ethical Issues

We anticipate a full board IRB approval, as this is a prospective study involving vitamins B₁ and C as the intervention. Appropriate patients will be approached and consented (often via proxy consent) by members of the research team. Patients will then be randomized by computer to receive vitamin C and vitamin B₁, or normal saline (control). The treating physicians, the research team, and the patients will all be blinded. The pharmacist mixing the drugs will be the only non-blinded team member.

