Data will be kept on an encrypted, password-protected computer behind two locked doors. Data will be managed by the investigators who will each have their own login.

Study Workflow

Patients admitted to the ICU who have severe sepsis or septic shock will be identified by the nursing staff, PAs, or physicians caring for them. These patients' consenting party will be approached within 24 hours of their presentation to the ED in an attempt to obtain informed consent. Following consent, the pharmacy will be notified of the study patient, randomization will occur, and the mixed medications (control or intervention) will be delivered to the patient's bedside in the ICU. Consented patients will receive 1.5g of vitamin C in 100mL of 0.9% sodium chloride (normal saline) every six hours for four days or until discharge from the ICU, whichever happens first (seventeen dose maximum). In addition, they will receive 200 mg IV vitamin B₁ every 12 hours in 100 mL of normal saline for four days or until ICU discharge (whichever happens first, nine dose maximum). Patients in the control arm will receive the 100 mL of 0.9% sodium chloride every six hours and 100 mL of 0.9% sodium chloride every 12 hours to act as placebos for the vitamin C and B₁ respectively. Doses up to 200 mg/kg/day were found to be safe in humans in one study.⁶ Several studies have been conducted in human subjects using IV vitamin B₁ and C, often at higher doses than proposed here, and have not seen serious side effects.^{10,12-14}

Some patients may receive hydrocortisone IV for refractory septic shock outside of this study protocol. This will be at the discretion of the treating physician and will not be included in the randomized and blinded intervention. Hydrocortisone has been shown in some studies to help

in patients with refractory septic shock.^{15,16} However, it is not uniformly employed. Patients receiving hydrocortisone will undergo a subgroup analysis to better elucidate the synergistic effects of hydrocortisone with vitamins B₁ and C.

After discharge, patients will be followed for 30 days to track hospital readmissions.

Reporting of Adverse Events

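### Hypothesis 2f, read literally, compares vitamin patients with and without discretionary hydrocortisone; that contrast is confounded by indication and, without the placebo arm, cannot show synergy

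*Combined protocol and SAP*

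**What the plan says.** - **Objectives.** Synergy is a stated aim: "we will investigate if there are benefits to those patients who also receive hydrocortisone in an effort to explore the synergistic relationship".
- **Hypotheses, secondary f.** Vitamin recipients who also get "IV hydrocortisone for refractory septic shock will have a more profound reduction in mortality when as compared to those receiving IV vitamins" B₁ and C without it. Both named groups receive vitamins; no placebo group is named.
- **Study Workflow.** "Some patients may receive hydrocortisone IV for refractory septic shock outside of this study protocol". On allocation: "This will be at the discretion of the treating physician and will not be included in the randomized and blinded intervention". The purpose of the analysis follows: "Patients receiving hydrocortisone will undergo a subgroup analysis to better elucidate the synergistic effects of hydrocortisone with vitamins".
- **Statistical Issues.** The subgroup is patients who get hydrocortisone against those who do not, with no time window. Fisher's exact test is the only mortality test named. The one regression planned concerns comorbidities. No interaction test and no adjustment for shock severity is mentioned.
- **Hypotheses, secondary e.** Patients on vitamins "will have fewer hours on vasopressors".

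**The concern.** Synergy is an interaction: the effect of vitamins with hydrocortisone compared with their effect without it. Estimating it needs placebo patients in both hydrocortisone strata. Literal 2f has none. It compares patients selected for refractory shock with patients who were not, so the difference mainly reflects why hydrocortisone was started. The bias runs against 2f: it can hide real synergy or make the combination look harmful.

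The phrase about a reduction in mortality also allows a second reading, vitamins against placebo within each hydrocortisone stratum. That keeps the randomised comparator. But because receipt has no time limit, use that begins after randomisation counts, and strata formed after randomisation are not protected by it. Vitamins may change who becomes refractory; hypothesis 2e expects fewer vasopressor hours. Blinding ("The treating physicians, the research team, and the patients will all be blinded") limits knowledge of the arm as a driver of hydrocortisone use, except where ICU staff are unblinded after an adverse event. It does not stop a treatment effect on shock from changing who receives it.

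The plan does not say which contrast is meant.

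**Working it through.** **Inputs.** From Enrollment/Randomization: 35% current mortality and 60 patients per arm. The plan gives no figure for this subgroup, so there is none to reproduce. Assumed, because the documents do not give them: the share *s* on hydrocortisone (20-50%) and user mortality *m*.

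**1. Literal 2f, neither treatment having any effect.** Non-user mortality is q = (0.35 − s·m)/(1 − s), and the gap is m − q. Example: s = 0.4, m = 0.5 gives q = (0.35 − 0.20)/0.60 = 25%, a gap of 25 points. The probability that Fisher's two-sided p ≤ 0.05 is by exact enumeration over 60 vitamin-arm patients.

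| User mortality | s = 20% | 30% | 40% | 50% |
|---|---|---|---|---|
| 35% (no sicker) | 0 points | 0 | 0 | 0 |
| 40% | 6.3 points; 5.7% | 7.1; 6.8% | 8.3; 7.8% | 10.0; 7.8% |
| 50% | 18.8; 19.9% | 21.4; 31.8% | 25.0; 45.4% | 30.0; 59.6% |
| 60% | 31.3; 47.8% | 35.7; 72.3% | 41.7; 90.1% | 50.0; 98.5% |

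In the first row the test is significant in 2.6-3.7% of trials. At m = 50-60%, significance with users *better* has probability at most 0.0006.

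**2. Masking.** Suppose vitamins truly cut mortality by 10 points, in hydrocortisone users only. The literal contrast is then the gap minus 10. At m = 50-60% users still look 8.8 to 40.0 points worse; at m = 40% they look only 0 to 3.8 points better.

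**3. Cross-check with a risk ratio.** Let hydrocortisone patients have 1.5 to 2.0 times the baseline risk: q = 0.35/(s·RR + 1 − s), for s = 20%, 35% and 50%. The null gap is 14 to 29 points, and Fisher's test is significant with users worse in 14-46% of trials. Example: s = 0.2, RR = 2 gives q = 0.35/1.2 = 29.2%, users 58.3%. If vitamins cut mortality by 40% in users only, users fall to 35.0%. The true interaction is −23 points, but the literal contrast is 35.0 − 29.2 = +6. Over the grid, true interactions of −17 to −23 points appear as −3 to +6.

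**4. Second reading (vitamins versus placebo within strata).** Assume vitamins have no mortality effect but cut hydrocortisone use from 40% to 30%. Let the sickest 30% die at 60%, the next 10% at 40%, and the rest at (0.35 − 0.18 − 0.04)/0.60 = 21.7%.
- Users: control (0.18 + 0.04)/0.40 = 55%, vitamins 60%; odds ratio 1.23.
- Non-users: control 21.7%, vitamins (0.04 + 0.13)/0.70 = 24.3%; odds ratio 1.16.
- Ratio of odds ratios: 1.06. Letting the sickest die at 50-70% and the next 10% at 30-50% gives 0.83 to 1.40.

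**5. Precision of the interaction.** SE of the log ratio of odds ratios = √(2·[1/(n₁·m(1−m)) + 1/(n₀·q(1−q))]), with n₁ = 60s and n₀ = 60 − n₁. For s = 20-50% and m = 35-60%, SE is 0.77 to 1.01, so the 95% CI extends exp(1.96·SE) = 4.5- to 7.2-fold each way. At s = 10%, SE is 1.22 to 1.28: 11.0- to 12.2-fold. On the risk-difference scale, two-sided 5% power for a 10-point interaction is about 7-9%.

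**The case against.** The strongest reply is that the literal reading is not the intended one. A reduction in mortality needs a comparator, and placebo is the only one in the design. Hypothesis 2g is built the same way, and read literally it would predict fewer deaths in high-SOFA than in low-SOFA vitamin patients, which is implausible. Statistical Issues also sets up the two arms before listing the subgroup analyses. On that reading the bias is small, of uncertain sign, and rests on an assumed fall in hydrocortisone use.

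The largest figures also come from the extreme corner: at 50% use and 60% user mortality, non-users would die at only 10%. False support for synergy is very unlikely under the literal reading when users are much sicker. The repaired analysis will be imprecise, and it narrows the question to hydrocortisone already in use at randomisation.

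Much of this stands. The within-strata reading is plausible, the corner values are illustrations, and the replacement will not settle the question. But the plan's wording names vitamins alone as the comparator and nowhere states the other contrast. Either way it sets no time window and names no interaction test. Hypothesis 2f is a listed directional hypothesis tied to an objective; the Objectives text speaks of exploring, but the plan does not label the analysis exploratory.

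**Conclusion.** The concern holds. Literal 2f cannot show synergy, because it has no placebo patients and its groups differ by indication; this follows from the design and not from the assumed figures. The size does depend on them: 19 to 50 points of spurious excess mortality if users die at 50-60%, 6 to 10 if they die at 40%, none if users are no sicker. That receipt counts at any time is inferred from the lack of a window. Under the second reading the result mixes effect modification with a selection effect that is small beside the interval's width. This should be corrected before analysis; the primary mortality comparison is unaffected.

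**What to change.** - Restate 2f as a vitamin-by-hydrocortisone interaction on mortality, in a logistic model using both arms, with hydrocortisone status taken at randomisation (already receiving: yes/no). State that the contrast concerns hydrocortisone already in use then.
- Report the interaction with a 95% CI and label it exploratory effect modification, not proof of synergy, because baseline hydrocortisone is not randomised and marks sicker patients.
- Report hydrocortisone started after randomisation by arm, as an outcome.
- Label any comparison by receipt at any time as descriptive and non-causal.

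**Cost.** Analysis wording plus one baseline field from the medication record. There are three downsides:
- The stratum is smaller than one based on receipt at any time.
- The CI is wide, as computed above, so the analysis can describe but not settle the question.
- The baseline no-hydrocortisone stratum will include later starters, since the "consenting party will be approached within 24 hours of their presentation to the ED in an attempt to obtain informed consent" and study drug runs for up to four days.

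On that last point, if half of 20-50% eventual users start later, they make up 0.10/0.90 = 11% to 0.25/0.75 = 33% of the stratum. Suppose vitamins have an odds ratio of 0.50 in all hydrocortisone users and 1 in everyone else. With 40% eventual use and users dying at 50%, mortality in the baseline no-hydrocortisone stratum is 31.3% on control and 27.1% on vitamins, odds ratio 0.82, so the ratio shrinks from 0.50 to 0.50/0.82 = 0.61. Across user mortality of 40-60% the range is 0.54 to 0.69.

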Due to the impact of the COVID-19 pandemic and associated restrictions and worry, it has been increasingly challenging to provide informed consent *in person* with legally authorized representatives. Hospital restrictions combined with a general reluctance of LAR's desire to come to the hospital and risk exposure makes in-person consent problematic. Consent will be obtained via one of two methods: (1) obtained in-person and documented by double signature, or (2) obtained telephonically with an additional hospital signatory witness. The research team will then memorialize written consent by post (mail) or electronic mail, when possible, but telephonic consent will be sufficient for recruitment of subjects and protocol start. If the consenting party is only available via phone, the study will be discussed with this Legally Authorized Representative, and additional family member as desired, thoroughly, and the research staff will then return a call at a reasonable interval, usually in two hours, to respond to any questions. Questions provided immediately will be answered in real time. During the two hour interval, the consent form will be faxed or emailed to the legally authorized representative for review. This telephonic consent will be witnessed by another member of the hospital team to ensure that the study is clear to the family member and all questions have been answered. We will then randomize the patient and begin treatment. If and when the subject has regained the mental capacity to participate in the informed consent process, s/he will be approached by the research staff and consented clarified. If the patient does not continue consent, they will be withdrawn from the study.

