The study personnel will report adverse events as soon as they become aware of them and within 24 hours of them being informed. All adverse events or unanticipated problems will be reported to the IRB. If the adverse event is thought to be related to the intervention, the medication will be stopped and the patient will be withdrawn from the study. They will be monitored closely for resolution of the adverse event. In order to ensure that the patient receives the ideal treatment for their adverse reaction and their newly-discovered allergy is documented appropriately, the research staff will un-blind the ICU staff and themselves. This will be accomplished by keeping duplicate sealed randomization envelopes. In the case of an adverse event, the research staff will open this additional envelope and inform the treating physicians.

Side Effects

Possible side effects for patients receiving IV vitamin C include diarrhea, nausea, vomiting, heartburn, headache, insomnia, and nephrolithiasis. Possible side effects for patients receiving IV vitamin B₁ include nausea, hives, wheezing, or angioedema. In the event of these reactions, the patients will be treated immediately for their allergic reaction by the primary team and will be withdrawn from the trial as previously mentioned.

Study Withdrawal

All patients who have a serious adverse event thought to be directly related to the intervention will be withdrawn from the study. The patient or their consenting proxy may revoke consent and withdraw from the study at any point as participation is completely voluntary.

Statistical Issues

The intervention arm (vitamin B₁ and C) and the control arm (sodium chloride 0.9%) will be compared statistically for demographics and patient characteristics; including age, gender, comorbidities, need for operative intervention, enteral nutrition, and Body Mass Index (BMI). Outcomes between these two groups will also be compared including hours of vasopressor use, ventilator days, HLOS, ICU LOS, comorbidities, renal function measured by patients' GFR and creatinine levels, procalcitonin levels, SOFA scores, discharge destination, readmission rates, and mortality rates. We will do a subgroup analysis of patients with septic shock as compared to those with severe sepsis. We will also do a subgroup analysis of the patients who receive hydrocortisone as opposed to those who do not.

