Fisher's exact test will be used to compare gender, operative intervention, rate of mortality and the 30-day readmission rate. Average BMI and average age will be evaluated via student's t-

test. Median number of ventilator days, average hours of vasopressor use, median daily SOFA scores, average procalcitonin levels, average creatinine levels, median GFR, median ICU LOS and median HLOS will all be compared via Mann-Whitney U test. A contingency table will be used to analyze the different types of enteral nutrition and patients' discharge destination. A multivariate regression analysis will be conducted to analyze patients' comorbidities.

Duration of Review

We will start recruiting patients on September 10, 2018. We expect recruitment and data collection to take 12 months. Data analysis and completion of a manuscript is expected to take another 12 months.

All data will be kept on a password-protected and encrypted computer located behind two locked doors. We will retain all data for three years after the completion of the study. Following this, all data will be deleted from the hard drive where they will be kept.

Publication Plan

We plan to write and submit a manuscript for publication in a peer-reviewed journal.

References

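### A related adverse event withdraws the patient from the study, not only from study drug, and no outcome follow-up is stated after that

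*Combined protocol and SAP*

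**What the plan says.** Three sections of the combined protocol and SAP deal with withdrawal after an adverse event.

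- **Reporting of Adverse Events:** an event "thought to be related to the intervention, the medication will be stopped and the patient will be withdrawn from the study". There is no severity condition. The next sentence gives the only subsequent follow-up: "They will be monitored closely for resolution of the adverse event". Research and ICU staff are then unblinded for that patient.
- **Side Effects:** after a list that includes mild reactions such as headache and insomnia, patients with these reactions "will be withdrawn from the trial as previously mentioned".
- **Study Withdrawal:** a narrower trigger. "All patients who have a serious adverse event thought to be directly related to the intervention will be withdrawn from the study" Revocation of consent by the patient or proxy follows as a further reason.

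Enrollment/Randomization uses the same term for a patient who regains capacity and declines: "If the patient does not continue consent, they will be withdrawn from the study".

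On follow-up, Study Workflow says: "After discharge, patients will be followed for 30 days to track hospital readmissions". It does not mention withdrawn patients. On analysis, the primary hypothesis is that treated patients "will demonstrate a decreased mortality rate compared to septic patients who do not receive IV vitamins", and Statistical Issues says: "Fisher's exact test will be used to compare gender, operative intervention, rate of mortality and the 30-day readmission rate". Neither place states who is in the comparison.

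**The concern.** Coming off study drug and leaving the study are different events. The first is a safety measure. The second normally ends data collection. The plan joins them for any event judged related, and uses the same term for patients who refuse consent. Site staff therefore have no wording that separates a patient who has stopped drug from one whose data may no longer be collected.

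The primary outcome is at stake. Withdrawal comes after randomisation and depends on reactions that the plan attributes to the vitamins, so it may be more frequent in that arm. Patients who react may also have a better or worse prognosis than the rest. If they drop out of the mortality comparison, the protection of randomisation is lost and the estimate can move either way.

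Unblinding adds to this. With no written rule, the choice to keep or drop such a patient could be made by people who already know the assigned arm.

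**Working it through.** **Text check**

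| Question | Where the plan touches on it | Answer given |
|---|---|---|
| Is withdrawal more than stopping drug? | Reporting of Adverse Events | Yes; both actions are listed |
| Which events trigger it? | Reporting; Side Effects; Study Withdrawal | Any related event; the listed reactions; serious and directly related events |
| What follow-up comes after it? | Reporting of Adverse Events | Until the event resolves |
| Are withdrawn patients in the 30-day follow-up? | Study Workflow | Not stated |
| Are they in the mortality comparison? | Statistical Issues | Not stated |
| Is there an intention-to-treat set or a missing-data rule? | No section | None |

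**Size of the possible bias**

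The plan gives no withdrawal rate, so there is no figure of its own to reproduce.

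Inputs from Enrollment/Randomization: 60 patients per arm, control mortality 35%, expected mortality on the vitamins 30%.

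Assumptions:
- There is no true effect, so mortality is 35% in both arms.
- A proportion w of an arm is withdrawn and left out.
- Mortality among the withdrawn is m, the same in both arms.

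Observed mortality in an arm after exclusion = (0.35 − w × m) / (1 − w).

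Example, vitamins arm, w = 0.10, m = 0.55: (0.35 − 0.055) / 0.90 = 32.8%. Control arm, w = 0.05, m = 0.55: (0.35 − 0.0275) / 0.95 = 33.9%. The spurious difference is 1.2 points from unrounded values.

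| Withdrawn, control vs vitamins | Observed mortality, m = 45% | Difference | Observed mortality, m = 55% | Difference |
|---|---|---|---|---|
| 2% vs 5% | 34.8% vs 34.5% | 0.3 | 34.6% vs 33.9% | 0.6 |
| 5% vs 10% (3 vs 6 of 60) | 34.5% vs 33.9% | 0.6 | 33.9% vs 32.8% | 1.2 |
| 10% vs 15% (6 vs 9 of 60) | 33.9% vs 33.2% | 0.7 | 32.8% vs 31.5% | 1.3 |
| 10% vs 25% (6 vs 15 of 60) | 33.9% vs 31.7% | 2.2 | 32.8% vs 28.3% | 4.4 |

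Differences are in percentage points, from unrounded values. With m = 25% or 15% they have the same size and the opposite sign. For example, 10% vs 25% withdrawn with m = 15% gives 37.2% vs 41.7%.

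The difference favours the vitamins if withdrawn patients die more often than average, and placebo if they die less often. It is zero if the same proportion, with the same mortality, is withdrawn from each arm.

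Equal rates alone are not enough. With 10% withdrawn from each arm but m = 25% in control and 45% on the vitamins, observed mortality is (0.35 − 0.025) / 0.90 = 36.1% vs (0.35 − 0.045) / 0.90 = 33.9%, a difference of 2.2 points.

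**Scale**

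The planned effect is 35% − 30% = 5 points. The standard error of the difference with 60 per arm at 35% is √(2 × 0.35 × 0.65 / 60) = 8.7 points, so the 95% half-width is 1.96 × 8.7 ≈ 17 points.

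**The case against.** The best case against the point is that nothing in the plan excludes withdrawn patients. The arms are compared as arms, Fisher's test is applied without stated exclusions, and a withdrawn patient stays under observation for the event. On this view the real gap is a missing analysis-population statement. That is partly right: the harm is conditional. But the withdrawal rule is an instruction to sites, and following it literally can lose the outcome data before any analysis set is defined.

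It can also be argued that the rule is meant only for serious or allergic reactions, as the Study Withdrawal section and the references to allergy suggest. The first sentence has no such limit, and conflicting triggers are themselves a reason to reword.

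On size, several objections stand:
- Relatedness is judged before unblinding.
- Reactions such as nausea can also occur on saline.
- Earlier studies are cited as showing no serious side effects.
- Most patients are expected to be sedated, so mild symptoms may go unreported.
- The 10% versus 25% case has no support in the documents. Without it, the table runs from 0.3 to 1.3 points, small beside a standard error of 8.7.

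Sampling error does not excuse a bias that a written rule would remove, but these points keep the matter modest.

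Two objections concern the remedy. The first is that using the broadest trigger throughout would stop drug in more patients. It would not: the first sentence already stops medication for any related event, while the serious-event sentence governs study withdrawal only. The second is that patients kept in follow-up will have been unblinded, so outcomes that depend on care, such as vasopressor hours, are then open-label. That stands and should be acknowledged in the report. Mortality is less exposed.

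**Conclusion.** The point holds. As written, a related adverse event of any severity takes the patient out of the study as well as off the drug, and no section secures mortality or other outcome data afterwards or says how such patients are analysed. The plan does not say that they will be dropped; it leaves that open.

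Under the stated assumptions, the spurious mortality difference is 0.3 to 1.3 points for the three lower pairs of withdrawal rates and up to 4.4 points for the highest pair, in either direction, against a planned effect of 5 points. The lower end is plausible in a largely sedated population. The amendment should be made because the remedy is cheap and the primary outcome is affected. Confidence in the practical size is only moderate, since every withdrawal rate used is an assumption.

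**What to change.** In Reporting of Adverse Events, Side Effects and Study Withdrawal, replace withdrawal from the study with permanent discontinuation of study drug. Use one trigger in all three places: the relatedness condition of the first sentence, without a seriousness requirement. The threshold for stopping drug then stays where it is.

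Add a sentence such as: *These patients stay in follow-up for mortality, 30-day readmission and all other outcomes and are analysed in their assigned arm, unless consent is revoked.* Reserve the term for study withdrawal for revoked or discontinued consent.

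The cost is a short amendment and continued collection of routine hospital data. In the scenarios above that means between about 4 patients (2% and 5% of 60: 1.2 + 3) and 21 patients (6 + 15). No extra patients or procedures are needed. Treatment and monitoring of the adverse event are unchanged.
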